# Changes made to original Protocol after trial commencement

18 th July 2013	Alternative recruitment strategy through single local advertisement (p.13). This was advised by the funder due to slower than planned recruitment. Approved as substantial amendment.
28 Dec 2014	Recruitment target reduced from 724 to 512 (p.4) and study end extended to 31st December 2016 (p. 4, 19, 20). Again, these changes were made because of slower than planned uptake by general practices and participant recruitment. Approved as minor amendment.
22 nd Dec 2014	Additional question (enquiring about development of new medical conditions in last two years) added to 24 month questionnaire, and blood pressure measurement added to final 24 month assessment (p.17). Approved as substantial amendment.
21 st May 2015	Addition of sub-study questionnaires concerning (1) perceived triggers to acute gout attacks and (2) joint pain, stiffness and function in regions not affected by acute attacks (p.15). Approved as substantial amendment.
26 th Nov 2015	Addition of incentives to attend for 24 month final assessment and completion of questionnaire (£25) and for completion of questionnaire alone (£15). Approved as substantial amendment.

An analysis plan was also made on 17 July 2013. Please see the further details of this plan at the end of this document

### **SYNOPSIS**

Title	Nottingham Gout Treatment Trial. Phase 2: Two Year Randomised Controlled Trial of a Nurse Led Package of Care		
Acronym	None		
Short title	Nottingham Gout Treatment Trial – Phase 2		
Chief Investigator	[name]		
Objectives	To determine in community-based patients with untreated or under treated gout the effectiveness and cost effectiveness of a nurse-led complex intervention that reflects recommended best practice (including urate lowering therapy (ULT) to reduce serum uric acid (SUA) levels to <360 µmol/l).		
Trial Configuration	Randomised, parallel group controlled trial comparing nurse led intervention with "standard" (GP led) care over a 2 year period  Multicentre study within the East Midlands and South Yorkshire (EMSY) Region.		
Setting	Primary Care, EMSY Region		
Sample size estimate	RCT: The sample size was estimated according to both primary and secondary outcomes. To achieve 90% power at 5% significant level (2-tailed), the sample size needed are: 70 patients for each group for reduction in SUA (primary outcome); 90 patients for each group for reduction in frequency of acute attacks in the final year, and 233 patients for each group for quality of life (QOL). Allowing a 10% drop-out rate over the 2 years, this requires a total of 512 patients (233 plus 36 dropouts in each arm) to provide adequate power for the primary outcome and for the 2 key secondary outcomes.		
Number of participants	Nurse intervention (RCT) – 256 Standard care (RCT) – 256		
Eligibility criteria	All – Adults aged 21 and over with GP diagnosis gout, confirmed following telephone interview to ensure that participants fulfil ACR criteria for gout.  Nurse intervention and standard care groups (RCT) – at least one acute attack of gout in the last year.		
Description of interventions	Nurse intervention arm – package of care based on best practice, including full information concerning nature and prognosis of gout, addressing illness perceptions of gout and possible barriers to care,		

Page **4** of **29** Final version 8 –18 May 2015

	individualised lifestyle modification advice and ULT to reduce SUA to below the saturation point for sodium urate crystal formation (360 µmol/L). Individuals in this group will be followed up regularly according to their clinical need/monitoring requirements.  Standard care/control participants will have a single nurse contact at baseline during which they will be provided with the Arthritis Research UK leaflet on gout and be informed on appropriate management of acute attacks. There will be no discussion on other aspects of gout management – if asked about lifestyle and ULT participants will be asked to question their GP about this. This group will be asked to provide a blood sample at 0, 12 and 24 months and also keep a diary of acute attacks over the next 2 years and complete a questionnaire (including QOL assessment) at 12 and 24 months.
Duration of study  Randomisation and blinding	Total – 3 years Per participant – 2 years Planned recruitment start date 1 January 2013 Study participants in the RCT will be aware that they have been randomised to either a nurse-led intervention or to continue standard care/GP-led management.
	Randomisation will be undertaken by the CTU using a web based, computer generated, stratified (by GP practice) random block system and undertaken by the CTU. Following randomisation participants and nurses will obviously both know which group they are in. Although participants will be aware that the study objective is to compare cost effectiveness of nurse versus doctor led management of gout they will not be informed prior to randomisation concerning the recommended best practice strategies which include ULT and treating to target.
Outcome measures	Primary outcome – SUA of <360 µmol/L at study end Secondary outcomes – reduction in number of self-reported acute attacks in year two; improved QOL scores (SF36, Gout Assessment Questionnaire - GAQ); reduction in tophus size and number; cost effectiveness and cost utility based on health utilisation cost and SF6D (derived from SF36).

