### Sample size and justification

### Sample size:

512 participants will be recruited for the RCT (this allows a 10% drop out over the 2 year period).

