### Power calculations:

Information that includes SUA on community-derived patients with gout is sparse. However, detailed information on frequency of attacks, treatment, SUA and quality of life is available for 250 gout patients from 17 practices in Nottingham (5, 11). In this survey: 30% of patients were on ULT; the rate for acute attacks in the previous year was 32% for patients on ULT and 57% for patients on no ULT; mean SUA was 318  $\mu$ mol/L in those taking ULT compared to 434  $\mu$ mol/L in those not taking ULT; and 23% of those taking ULT had a SUA >360  $\mu$ mol/L, compared to 75% of those not on ULT. For quality of life (SF36) overall mean and SD for those on ULT was 16.41 (2.81) compared to 15.67 (3.05) for those not on ULT, giving a pooled SD of 3.09 and a mean difference of 0.7 between groups (the latter is used as a proxy of effect size d).

According to these results, we have estimated the following sample size requirements, to achieve 90% power at 0.05% significance level, for each outcome:

- reduction in frequency of acute attacks in final year a sample size of 90 is required for each arm
  - reduction in SUA below the therapeutic target a sample size of 70 patients is required for each arm
- quality of life a sample size of 233 is required for each arm (80% power at 0.05% significance level

Allowing a 10% drop-out rate over the 2 years, this requires a total of **512 patients** (233 plus 23 dropouts in each arm) to provide adequate power for the primary outcome and for 2 of the key secondary outcomes. There are no data on changes in GAQ in response to treatment, but being a disease-specific instrument, we assume that the GAQ will be more sensitive to change than the SF36 and that a total size of 796 will be adequately powered for this outcome.

The total number of GP practices in Nottinghamshire is 170 and the estimated number of registered patients with gout is 10,720 (i.e. an average of 65 patients per GP). A questionnaire will be sent to all patients (unless they have an exclusion criterion) to detect eligible patents. A random sample of those eligible will be selected using the simple random selection after the consent to the trial.

Page **20** of **29** Final version 8 –18 May 2015

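### The version 8 synopsis builds 512 from 233 plus 36 dropouts per arm, which sums to 538; the body's 233 plus 23 does give 512 but leaves about 230 completers per arm at 10% dropout

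*Supplement*

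**What the plan says.** Protocol version 8 explains its total in three places.

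- **Synopsis, Sample size estimate.** The largest requirement is "233 patients for each group for quality of life (QOL"), and the total follows from it after a 10% allowance for dropout over two years: "this requires a total of 512 patients (233 plus 36 dropouts in each arm) to provide adequate power". The next row, Number of participants, gives 256 for each arm.
- **Sample size and justification, Sample size.** "512 participants will be recruited for the RCT (this allows a 10% drop out over the 2 year period").
- **Sample size and justification, Power calculations.** The same requirement of 233, the same 10% and the same total of 512 appear, but itemised as "233 plus 23 dropouts in each arm".

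Both itemisations stand in the latest version. The requirements for the other two outcomes are 70 per arm (serum uric acid target, primary) and 90 per arm (acute attacks), so quality of life alone sets the size of the trial.

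**The concern.** One requirement, one dropout rate and one total cannot produce two dropout allowances. The synopsis bracket does not add up to the total beside it or to the per-arm number in the row below. A reader who tries to reproduce the trial's size from the synopsis will fail.

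The allowance is also the benchmark for judging loss to follow-up over two years, so it should be clear and correct. If 233 means patients with 24-month data, the number randomised should be the number that leaves 233 after 10% are lost. That is a different calculation from adding 10% to 233.

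What is at stake is small: whether the sample-size statement can be reproduced, and a few completers on a secondary outcome.

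**Working it through.** **Inputs (protocol version 8).** Required per arm for quality of life: 233. Dropout: 10% over two years. Dropouts added per arm: 36 (synopsis), 23 (Power calculations). Randomised: 256 per arm, 512 in total.

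**1. Reproducing the total**

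| Source | Sum per arm | Total | Added dropouts as share of arm |
|---|---|---|---|
| Body: 233 + 23 | 256 | 512 | 23/256 = 9.0% |
| Synopsis: 233 + 36 | 269 | 538 | 36/269 = 13.4% |

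The body reproduces 512. The synopsis misses it by 538 − 512 = 26.

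**2. Where the 36 may come from.** The version 4 synopsis has 326 plus 36 = 362 per arm, 724 in total. There the 36 fits the 10% rate: 36/362 = 9.9%, and 326/0.90 = 362.2. In version 8 the 326 became 233 and the 724 became 512, but the 36 is unchanged. That it is a leftover is an inference; no document says so.

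**3. Allowing for dropout.** With dropout rate d, the number to randomise is n/(1 − d).

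- Division: 233/0.90 = 258.9, so 259 per arm and 518 in total (about 26 dropouts per arm).
- Addition, as the body appears to have done: 233 × 1.10 = 256.3, used as 256.
- Expected completers from 256: 256 × 0.90 = 230.4, about 2.6 short of 233.
- Loss that 256 can bear before falling below 233: 23/256 = 9.0%.
- Gap in total: 518 − 512 = 6 patients, 6/512 = 1.2%.

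**4. Cost in power for quality of life.** Two-sample t-test, two-sided 5%. The first two rows use SF36 figures from Power calculations: SD 3.09, with a difference of 0.70 (as printed) or 0.74 (16.41 − 15.67). The third uses the standardised effect implied by version 4's 326 per arm at 90% power: √(2/326) × (1.960 + 1.282) = 0.254. It is computed with the normal approximation.

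| Effect | Power at 233 | Power at 230 | Loss (points) |
|---|---|---|---|
| 0.70/3.09 | 68.4% | 67.9% | 0.5 |
| 0.74/3.09 | 73.2% | 72.7% | 0.5 |
| 0.254 | 78.2% | 77.7% | 0.5 |

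The level depends on the effect assumed; the loss does not, to the precision shown.

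**5. Other outcomes.** 230 is well above the 70 per arm for the primary outcome and the 90 per arm for attacks.

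**The case against.** The strongest reply is that the enrolment target is never in doubt. It is 512 in the synopsis and in both sample-size paragraphs, the synopsis gives 256 per arm, and the body's itemisation adds up. On that view the 36 is a slip of the pen. This largely stands, and it is why the point is minor, but nothing in version 8 corrects the bracket.

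The difference between adding 10% and dividing by 0.90 is also, fairly, called trivial: 6 patients in 512. In addition, the analysis plan puts all three time points into one multilevel model, so a patient lost after 12 months still contributes data and the effective loss may be smaller than a count of completers suggests. That is right, and it weakens the second part further. The sample-size statement is nevertheless written in terms of dropouts, so its figures should agree on that basis.

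A further objection is that printing 230 expected completers beside a requirement of 233 advertises a shortfall. It does, but the shortfall already exists, and quoting power at 230 reports it honestly.

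Two stronger readings are tempting and should be resisted.

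- A reader might infer that neither dropout figure secures 233 completers. That is not so. If 269 per arm were really enrolled, 10% loss would leave 269 × 0.90 = 242, above 233. Only the 256 actually planned falls short.
- A reader might subtract 36 from 256 and conclude that the trial expects 220 completers, about 14% attrition. No passage states such a rate; the only rate given is 10%, and the 36 does not belong to an enrolment of 256.

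**Conclusion.** The point holds as a minor one. The synopsis bracket is certainly wrong: it sums to 538, not 512, and contradicts both its own 256 per arm and the body's 23.

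The inflation error is real but small. At 10% dropout the trial can expect about 230 completers per arm instead of 233, at a cost of about 0.5 percentage point of power for quality of life. This reads 233 as the number needed with 24-month data and takes dropout as exactly 10% in each arm. The primary outcome, the attack outcome and the enrolment target are unaffected.

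The power levels of 68% to 78% in the table should not be blamed on dropout. They reflect the effect size and SD assumed. Whether 233 delivers the 80% power stated for it in Power calculations, or the 90% under which the synopsis lists it, is a separate question that this check does not settle.

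**What to change.** Keep 512. Remove the 36 from the synopsis so that it agrees with the body. In both the synopsis and Power calculations, replace the itemised dropouts with one statement: 512 randomised, 256 per arm; at 10% dropout (about 26 per arm), about 230 per arm are expected to complete 24 months. Quote the quality-of-life power at 230 per arm and name the effect size and SD used.

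The cost is a wording change in two sections. No extra patients are needed and the analysis does not change. The only price is that the stated number of completers becomes slightly less favourable, 230 in place of 233.

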# Statistical methods Intention to treat (ITT) analysis will be undertaken to compare treatment effects between groups. Multi-level models will be used to handle any missing outcome measures. Chi-square test will be used for dichotomous or categorical data and ANOVA test will be used for continuous variable. Adjustment will be made for baseline co-variables as appropriate using multiple regression models. Cost per quality adjusted life year (QALY) will be estimated.

### **ABBREVIATIONS**

Add to / amend accordingly

ADR Adverse Drug Reaction

AE Adverse Event

BSR British Society for Rheumatology

CI Chief Investigator overall

CRF Case Report Form
DAP Data Analysis Plan

DMC Data Monitoring Committee

EMSY East Midlands and South Yorkshire regions

EOT End of Trial

EULAR European League Against Rheumatism

GAQ Gout Assessment Questionnaire

GCP Good Clinical Practice

GPRD General Practice Research Database

ICF Informed Consent Form

ITT Intention to Treat analysis

NHS National Health Service

P/GIS Parent / Guardian Information Sheet

PI Principal Investigator at a local centre

PIS Participant Information Sheet

QALY Quality Adjusted Life Year

QOF Quality and Outcomes Framework

QOL Quality of Life

RCT Randomised Controlled Trial

REC Research Ethics Committee

R&D Research and Development department

SAE Serious Adverse Event

SPC Summary of Product Characteristics

SUA Serum Uric Acid

TMG Trial Management Group
TSC Trial Steering Committee
ULT Urate Lowering Therapy

Page **7** of **29** Final version 8 –18 May 2015

### TRIAL / STUDY BACKGROUND INFORMATION AND RATIONALE

Gout is a chronic disabling condition caused by urate crystal deposition. It affects 1-2% of UK adults and is the most common inflammatory arthritis in men and the most common inflammatory arthritis in older women (1, 2). The prevalence increases with age to 7% of men aged >65 and to 3% of women aged >85. Unlike other common forms of arthritis we have a good understanding of gout pathogenesis and have effective strategies and treatments to eliminate the causative agent (i.e. urate crystals) and thus "cure" the disease.

Gout is predominantly managed in primary care. However, the treatment of patients with gout is often suboptimal (3-5). Two recent UK studies, one involving the General Practice Research Database (GPRD) and one an epidemiological study in Nottingham (3, 5), suggest that only one third of patients receive urate lowering therapy (ULT) and that this is inevitably allopurinol. Even when ULT is given it is usually prescribed at a single fixed dose (allopurinol 300 mg daily) that is insufficient for many patients, and without any monitoring of renal function or serum uric acid (SUA) to confirm that the therapeutic target of reducing SUA levels to well below the saturation point for crystal formation (360 µmol/l) has been achieved. The dose of 300mg daily is insufficient for many younger patients with normal renal function, but too much for some older people with renal impairment. Furthermore, very few patients receive information on gout or appropriate advice to modify lifestyle to reduce predisposing risk factors. As a consequence of such management only a minority of patients (<25%) become free of gout attacks, the majority continuing to experience acute attacks and being at risk of progression of their disease and developing irreversible secondary joint damage (6).

To improve current practice, the British Society for Rheumatology (BSR) and the European League Against Rheumatism (EULAR) have developed evidence-based recommendations for management of gout (7, 8). Notwithstanding the absence of randomised controlled trial (RCT) evidence that any intervention reduces the incidence of recurrent gout there is strong consensus on the components of management that will reduce the incidence of recurrent gout (9). Specifically, this is combining patient education and lifestyle advice with appropriate use of ULTs to achieve a target SUA level of  $\leq$ 360  $\mu$ mol/l. These elements will form the components of a complex intervention (10).

Whilst these elements have not been shown individually to be effective at reducing recurrent gout, there is good reason, based on knowledge of disease pathogenesis and clinical experience, to believe that such a package has the potential to reduce the incidence of recurrent gout, to reduce the size of tophi (hard palpable lumps of urate crystals which build up under the skin) and to improve quality of life (QOL). However, in phase 1 of the Nottingham Gout Clinical trial we have undertaken a "proof of concept" study in which 106 sub-optimally treated, community-derived patients with gout were managed by [name] (who saw all patients at their first visit) but subsequently predominantly managed by a trained specialist nurse for one year. At the end of the year the therapeutic target was achieved in 92% of patients. We have also undertaken qualitative work to examine illness perceptions and possible barriers to care in patients with gout and these data have informed the development of the nurse led intervention and the training programme that will be required for the nurses that will deliver it. An RCT is now required to determine the effectiveness of implementing such a strategy and to demonstrate improvement in patient-centred outcomes (reduced frequency of attacks, improved QOL, reduction in size and number of tophi, if present) as a consequence of successful gout management

Despite the existence of evidence based guidelines on management and "cure" of gout it is apparent that it is difficult to alter the behaviour of GPs by education alone and that financial

Page **10** of **29** Final version 8 –18 May 2015

incentives through a QOF (Quality and Outcomes Framework) are the most effective way of improving the standard of care for a specific condition. Gout would seem ideal for a QOF in that there is a simple measure for standard of care (SUA) and practical national and international guidelines concerning management. The one requirement that is missing is data demonstrating improved QOL as a consequence of successful management. Should we be successful, data obtained from this RCT will be used in a submission to the Department of Health to consider making gout a QOF. Should this happen there will be a significant improvement in the standard of care of the millions of gout sufferers who are currently treated sub-optimally. Furthermore, data from our study could be used to support nurses taking the lead in delivery of gout care, following standard protocols, in the community.

### TRIAL / STUDY OBJECTIVES AND PURPOSE

### **PRIMARY OBJECTIVE:**

To determine in community-based patients with untreated or under treated gout the effectiveness and cost effectiveness of a nurse-led complex intervention compared to standard GP led care.

### TRIAL / STUDY DESIGN

### TRIAL / STUDY CONFIGURATION

This will be a conventional, multicentre, randomised parallel group controlled trial in the EMSY Region comparing, over a 2 year period, the outcomes in patients with gout who receive either (1) a nurse-led package of care reflecting current recommendations or (2) continuing GP led standard care (plus an initial single visit with a nurse to receive an information leaflet and discussion focused just on acute attacks).

The overview of the design of the RCT has been developed according to the MRC framework for complex intervention.

### **Primary endpoint:**

Percentage of patients who hit the therapeutic target at end of year 2 (SUA <360 µmol/L)

### **Secondary endpoints:**

Percentage with reduction of frequency of acute attacks in the second year. Difference in QOL scores for SF36 and GAQ at end of study.

Percentage with reduction in size of the largest index tophus and reduction in number of tophi.

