### Assessment will involve:

**Enquiry:** age, sex, gout history (onset, acute attacks/frequency/sites affected/chronic symptoms), drug history (allopurinol/start date/dose, diuretics/duration; other drugs), family history comorbidities (most detailed first visit), completion of a QOL questionnaire (generic - SF36; and disease-specific - the gout assessment questionnaire (GAQ)) at the end of year one and again at the end of year 2. The questionnaires will take approximately 20 minutes to complete. Participants' blood pressure will also be checked at the end of year 2.

**Examination**: tophi (sites); height, weight (BMI).

**Investgations**: serum uric acid, GFR, creatinine.

If tophi are present, the maximum diameter of the longest tophus will be measured using a Vernier calliper and the total number and site of tophi will be recorded.

All investigations will only be undertaken to assist clinical assessment. Individuals participating in the study will receive a package of care based on current recommended quidelines.

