### **STATISTICS**

### Methods

The trial statistician ([name]) will oversee the data management, evaluation and analyses. The database will be developed in collaboration with the CTU using access and analysed using SPSS. SUA will be analysed at baseline, 12 months and 24 months. Comparison will be undertaken between the nurse led intervention and control at each observational point. There will be no interim analyses for efficacy or safety. Intention to

Page **19** of **29** Final version 8 –18 May 2015

treat (ITT) analysis will be undertaken to compare treatment effects between groups. Multilevel models will be used for any missing outcome measures. Chi-square test will be used for dichotomous or categorical data and ANOVA test will be used for continuous variables. Adjustment will be made for baseline co-variables as appropriate. Cost per QALY will be estimated from the SF6D and the direct and indirect costs related to gout and its management.

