### **Secondary Efficacy Endpoints:**

Percentage in each group with reduced number of acute attacks in the second year of the study

Quality of life scores (SF36 and GAQ) at end point compared to baseline in each group and comparison of endpoint QOL scores between the two groups.

Reduction in size and number of tophi.

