# 2. Secondary outcomes

- Number of acute attacks in preceding year, year 1 and year 2 within each group and between groups
- Number of patients with tophi at baseline, 12 months and 24 months with each group and between groups
- Mean QoL scores (overall, different domain scores of SF36 and the Gout
   Asssessment Questionnaire (GAQ) including the Gout Impact Scale (GIS) of the GAQ.
   at 0, 12 and 24 months within each group and between groups
- Mean change of QoL scores from baseline to 12 months and 24 months within each group and between groups

**Covariates and baseline predictors:** age, gender, body mass index, disease duration, tophi, associated comorbidity etc.

Task allocation and timetable: The Nottingham CTU will undertake randomisation, development of the database for RCT and the web-based data entry platform. CTU will also conduct data monitoring and quality control for the RCT data. Academic Rheumatology will recruit patients, enter the data through a web-based data entry platform for the RCT data and develop an independent database for the observational group. Both datasets are not open for any interim analysis between baseline and 24 months to keep the randomisation. Analysis will start after 24 months when the data has been fully completed, quality checked over and closed. Analysis for clinical effectiveness (efficacy and side effects) will be completed in 3 months after the closing date of the data. Analysis for cost-effectiveness will be completed in 12 months, as it requires acquisition of additional data for cost. In brief:

- Recruitment 8 months
- RCT and observation 24 months
- Results for clinical effectiveness 3 months
- Results for cost-effectiveness 12 months

Economic Analyses Plan.

Two economic analyses are planned: the first being an economic analysis alongside the RCT and the second modelling the costs and benefits over a longer time horizon. The base case in both models would use an NHS perspective, with a societal perspective (that include indirect costs such as lost productivity) being undertaken in a sensitivity analysis.

Economic analysis alongside the RCT

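### The tophus-size endpoint counts any fall in diameter as a reduction; analysing the measured change in diameter would avoid noise responders and keep more power

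*Supplement*

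**What the plan says.** The protocol (version 8, Secondary endpoints) gives the endpoint as "Percentage with reduction in size of the largest index tophus and reduction in number of tophi". Under Assessment of Efficacy, Secondary Efficacy Endpoints, it becomes "Reduction in size and number of tophi", without a percentage. The measurement is described under Nurse intervention, Assessment will involve: "the maximum diameter of the longest tophus will be measured using a Vernier calliper". None of these places gives a minimum change, a duplicate reading, a recording unit, an expected reading error or a rule that the same observer reads twice.

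The Methods section says "Chi-square test will be used for dichotomous or categorical data" and assigns ANOVA to continuous variables. The analysis plan of July 2013 lists one tophus outcome under Secondary outcomes, "Number of patients with tophi at baseline, 12 months and 24 months with each group and between groups", and nothing on size. The power calculations cover serum uric acid, acute attacks and quality of life. No response rate, power or expected number of patients is given for tophi.

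**The concern.** If the only test of response is whether the later reading is below the earlier one, a fall of a fraction of a millimetre counts the same as complete disappearance. A stable lump read twice with error will often read lower the second time. The reported percentage would then credit both arms, standard care included, with some shrinkage that did not occur, and the difference between arms would narrow.

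Separately, a measured length reduced to yes or no at zero loses information. Only patients with a tophus can contribute, so the evaluable group may be much smaller than the 256 randomised per arm.

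**Working it through.** The plan states no tophus figure, so there is nothing to reproduce. All numerical inputs below are assumptions. The documents supply only the definition, the calliper method and, from the Synopsis, the two-sided 5% level.

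**1. False reductions in an unchanged tophus.** Take two readings of the same lump with independent, symmetric error. Then P(decrease) = (1 − P(tie))/2. Results with normal error and true diameters spread over 5 to 30 mm:

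| Recorded to | Error SD 0.25 mm | 0.5 mm | 1 mm | 2 mm |
|---|---|---|---|---|
| 0.1 mm | 44% | 47% | 49% | 49% |
| 1 mm | 14% | 26% | 36% | 43% |

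For example, at 1 mm and SD 0.25 mm ties occur in 71.8%, so (1 − 0.718)/2 = 14%. At 0.1 mm and SD 2 mm ties occur in 1.4%, so (1 − 0.014)/2 = 49%.

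True growth g lowers the rate. For a continuous reading it is Φ(−g/(SD√2)). With g = 1 mm this gives 8%, 24% and 36% at SD 0.5, 1 and 2 mm.

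**2. Dilution.** Let f be the false-reduction rate among tophi that do not truly shrink, and suppose true shrinkers always register. The observed rate is p + (1 − p)f, so the difference between arms is multiplied by (1 − f). Take true rates of 20% v 50% and f = 0.25:

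- Standard care: 0.20 + 0.80 × 0.25 = 40%.
- Nurse arm: 0.50 + 0.50 × 0.25 = 62.5%.
- The 30-point difference becomes 22.5 points, and power at 30 per arm falls from 69% to 41%.

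**3. Any reduction against mean change.** Assume 30 tophaceous patients per arm, mean shrinkage 2 mm v 0, SD of true change 2 mm, error SD 1 mm per reading, and normal distributions.

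- SD of observed change: √(2² + 2 × 1²) = 2.45 mm.
- P(reduction): Φ(0) = 50% in standard care; Φ(2/2.45) = 79% in the nurse arm.
- Power of the chi-square test on any reduction: 67% by exact enumeration (68% by simulation).
- Power of the t-test on mean change, standardised difference 2/2.45 = 0.82: 88%.

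The number of tophaceous patients is unknown. At 20 per arm the same comparison gives 51% v 71%, and at 50 per arm 88% v 98%.

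**4. How much of the gap is calliper error?** Set the error to zero. The SD of change is 2 mm and the nurse-arm rate is Φ(2/2) = 84%. Power at 30 per arm is then 82% for any reduction and 97% for mean change. The gap is about 15 points with a perfect calliper and about 21 points with error SD 1 mm. At 1.5 mm mean shrinkage the figures are 60% v 81% without error and 45% v 65% with it. Most of the loss is the cost of dichotomising.

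**The case against.** A reader might infer that noise alone turns a quarter to a half of patients into responders in both arms. The documents do not support that. They give no reading error and no recording unit, and 14% is as consistent with them as 49%. The rate applies only to patients with a tophus that has not truly changed. In the nurse arm many tophi are expected to shrink, and the protocol describes tophi under continuing deposition as slowly enlarging.

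A reader might also infer regression to the mean, which could lift the rate above 50%. That requires the lesion picked as largest at baseline to be the one remeasured. One passage speaks of an index tophus and another only of the longest. If whichever is longest is measured at each visit, the two readings are exchangeable when nothing changes and the rate cannot exceed 50%.

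It is tempting, too, to blame the whole power gap on the calliper. Step 4 shows that most of it remains without any error.

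Further points stand for the plan. The second statement of the endpoint has no percentage, and both documents provide methods for continuous outcomes, so an analysis of change is not excluded. Noise that is equal in both arms dilutes a difference but does not inflate the type I error. The endpoint is secondary and was not powered.

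What remains is that the one explicit definition is a percentage with any reduction, and that the analysis plan has no size outcome to replace it.

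**Conclusion.** The point holds as a low-priority improvement in the choice of analysis. Read literally, an unchanged tophus is counted as reduced with a probability of about 14% to 49% over the error SDs and recording units tried, approaching 50% when ties are rare and falling if the tophus truly grows. This dilutes the contrast between arms. Dichotomising at zero costs about 21 points of power in the worked example, about 15 of them unrelated to calliper error.

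These sizes rest on assumed values for the number of tophaceous patients, the shrinkage, its SD and the reading error, and on normal changes. Frequent complete resolution would skew the changes and alter the exact figures. The direction is firmer: mean change had more power than any reduction in every setting tried. The primary serum uric acid conclusion is not affected.

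**What to change.** In the protocol's Secondary endpoints and Secondary Efficacy Endpoints, and in the analysis plan's Secondary outcomes, define the size endpoint as follows: the between-arm difference in change of diameter (mm) of the same index tophus identified at baseline, adjusted for baseline diameter, in patients with a tophus at baseline, with a resolved tophus counted as 0 mm. The linear multilevel model already in the analysis plan can carry this. Report the percentage with any reduction, or with complete resolution, as descriptive support only.

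A responder cut at the limit of calliper repeatability is not a substitute. In an example with 20% v 70% truly shrinking, 30 per arm and error SD 1 mm, a cut at 1.96 × √2 × 1 = 2.77 mm raised power from 56% to 92% when the mean shrinkage was 5 mm, but lowered it from 38% to 33% when it was 2 mm. It would also need duplicate readings, which the protocol does not specify.

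The cost is wording only, because the change uses the same calliper readings that the percentage needs. The downside is a headline in mm rather than a percentage.
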